HRPO Protocol

1) Protocol Title (Version # and/or Version Date)

The Emotions and Decisions of Couples, #12-433, v. 06/13/2018

2) IRB Review History

N/A

3) Objectives

The proposed study is an experimental comparison of the effects of alcohol on arousal and emotion-regulation between 112 Distressed Violent (DV) and 112 Distressed Nonviolent (DNV) partners. One partner from each DV couple will be pseudo-randomly selected and yoked to a DNV partner of the same sex and a relationship satisfaction within a five-point range for participation in the experiment. To test the overall hypothesis that over-arousal is a mechanism through which alcohol is associated with increases in the frequency and severity of IPV, the selected partners will participate in a counter-balanced placebo session and alcohol administration session during which EEG, psychophysiology and pupillary response measurements of arousal will be collected during an emotion regulation task.

Specific Aim 1: To determine if normal increases in arousal after alcohol exposure is potentiated by evocative partner stimuli is greater for distressed violent (DV) partners compared to distressed nonviolent (DNV) partners. *Hypothesis 1a:* DV and DNV partners will experience comparable alcohol related increases in arousal. *Hypothesis 1b:* DV partners will demonstrate greater arousal increases by evocative partner displays than DNV partners. *Hypothesis 1c:* DV partners will experience greater arousal when exposed to alcohol and evocative partner stimuli than DNV partners.

Specific Aim 2: To determine if alcohol induced arousal interferes with DV partners' ability to regulate emotion in response to evocative partner stimuli compared to DNV partners. *Hypothesis 2a:* Emotion regulation during evocative stimuli will be reduced compared to neutral stimuli. *Hypothesis 2b:* Emotion regulation during evocative stimuli will be reduced by alcohol. *Hypothesis 2c:* DV partners will be less able to regulate emotion during evocative stimuli than DNV partners. *Hypothesis 2d:* Alcohol will interfere with DV partners' ability to regulate emotion during evocative stimuli compared to DNV partners.

4) Background

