Participants will be a convenience sample of 112 DV couples and 112 DNV couples residing in the greater Albuquerque, NM metro area. Eligible couples will be 1) English-speaking, 2) heterosexual or homosexual, 3) between the ages of 21 and 45, and will provide informed consent. Because this is a study of the role of alcohol in IPV, all participants (DV & DNV) must 4) be in a distressed relationship (Revised Dyadic Adjustment Scale score below 47), 5) consume at least one to two alcoholic drinks per sitting each week for females and three to four alcoholic drinks for males, 6) report two binge drinking episodes (>4 drinks for males, >3 drinks for females) in month prior to assessment, 7) be married or cohabitating for at least six months, 8) both partners must be willing to participate, 9) must have a breath alcohol level of 0.0 g% at all visits. DV couples must have a history of at least mild physical aggression in the past six months (e.g., twisted partner's arm or hair). Participants will be excluded if they are/have 1) currently separated, 2) an order of protection in place, 3) facing violence-related criminal charges, 4) currently in a domestic violence shelter, 5) evidence of psychosis or severe personality disturbance, 6) pregnant, 7) taking a medication contraindicated for use with alcohol, 8) currently taking insulin or oral hypoglycemic medication, 9) an AUDIT score greater than 19 indicating alcohol dependence, 10) illicit drug use (except marijuana), or 11) provide a positive UA at first emotion-regulation session. Participants will be screened for psychosis and severe personality disturbance using the SCID II psychosis and personality screeners. The age range reflects legal drinking age and age range used in other studies of alcohol and IPV (Eckhardt, 2007). The minimum length of relationship is to obtain a representative sample of DV couples. DV relationships are exceptionally unstable and dissolve at rates many times that of DNV relationships (Gortner et al., 1997). It is feared that older DV relationships may not be representative of DV relationships (e.g., less violent, Cui et al., 2013).

Adults unable to consent, individuals who are not yet adults, pregnant women and prisons will be excluded.

6) Number of Subjects (Recruitment Target)

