Specific Aim 1: To determine if normal increases in arousal after alcohol exposure is potentiated by evocative partner stimuli and is greater for DV partners compared to DNV partners. We will conduct a 2 (beverage condition: alcohol vs. placebo) x 2 (stimulus: evocative vs. neutral) repeated measures ANOVA with a between-subjects factor (partner type: DV vs. DNV). To test whether alcohol increases overall arousal (**Hypothesis 1a**), we will examine the main effect of alcohol vs. placebo on arousal variables, collapsing across partners and stimuli during the WATCH condition as alcohol should effect the arousal of both partner types equally. To test whether DV partners are more aroused by evocative partner displays than DNV partners (**Hypothesis 1b**), we will test the interaction effect of partner type and stimulus type, collapsing across alcohol and placebo conditions. Finally, to test the hypothesis that alcohol induced increases in arousal above placebo will be greater for evocative than neutral stimuli (**Hypothesis 1c**) for DV vs. DNV partners, we will test the three-way interaction in the 2 (DV vs. DNV) x 2 (alcohol vs. placebo) x 2 (evocative vs. neutral) repeated measures ANOVA. Specifically, this contrast will examine the effect of partner type when comparing stimuli type (evocative) to beverage condition (alcohol) on arousal and provides a critical control given that conflict intensity may differ between DV and DNV couples. The 3-way interaction (Hyp1c) will allow us to be able to determine whether the change in arousal between alcohol and placebo sessions for the evocative stimuli differs between couple types. The arousal level of evocative stimuli is matched between alcohol and placebo sessions, thus allowing for a controlled examination of alcohol-induced increases in arousal for evocative stimuli across DV and DNV couples.

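### Hypothesis 1a is stated as comparable alcohol effects in DV and DNV partners, but its only assigned test is the beverage main effect, which does not estimate the DV-DNV difference (minor)

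*Combined protocol and SAP*

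**What the plan says.** Section 3, Specific Aim 1, states H1a as: "DV and DNV partners will experience comparable alcohol related increases in arousal". In the Data Analysis Plan of Section 14, the H1a label is attached to a different question: "To test whether alcohol increases overall arousal". The test is described thus: "we will examine the main effect of alcohol vs. placebo on arousal variables, collapsing across partners and stimuli during the WATCH condition". The reason given for collapsing is "as alcohol should effect the arousal of both partner types equally".

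The Aim 1 model is a 2 (beverage) x 2 (stimulus) repeated measures ANOVA with partner type between subjects. It therefore contains a partner type x beverage term. H1b is assigned the partner type x stimulus term and H1c the three-way term. No hypothesis is assigned to partner type x beverage. Neither section gives a margin, an interval criterion or any other rule for calling two responses comparable.

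H1c is worded in three ways. Section 3 says that DV partners will be more aroused than DNV partners under alcohol combined with evocative clips. Section 14 first defines H1c, for DV versus DNV partners, as "alcohol induced increases in arousal above placebo will be greater for evocative than neutral stimuli". It then says the three-way term will determine "whether the change in arousal between alcohol and placebo sessions for the evocative stimuli differs between couple types".

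**The concern.** Comparability is the hypothesis in Section 3 and an untested premise in Section 14. If the H1a result is reported against the Section 3 wording, a significant main effect would be read as support for comparable responses, even if one group responded to alcohol much more than the other. The study measures arousal in several ways ("EEG, psychophysiology and pupillary response measurements of arousal will be collected during an emotion regulation task"), so this could happen for each arousal variable.

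The H1c wording is a separate but related matter. The three-way term compares evocative with neutral clips. It does not by itself show the DV-DNV difference on evocative clips, which is what the last Section 14 sentence says it shows.

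**Working it through.** **Inputs from the documents.** 112 DV and 112 DNV partners (Section 3); the Aim 1 model and assigned tests (Section 14). The plan gives no power figure for these terms, so there is none to reproduce.

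**Assumed inputs.** Two-sided 5% tests; SD of the alcohol-minus-placebo change, averaged over WATCH trials, equal to 1 in both groups; no dropout; groups independent unless stated.

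**1. What each contrast estimates.** Let d_DV and d_DNV be the mean alcohol-minus-placebo changes over WATCH trials.
- Beverage main effect: (d_DV + d_DNV)/2.
- Comparability (partner type x beverage): d_DV - d_DNV.
- Covariance of the two estimates: (Var_DV - Var_DNV)/2, where each Var is the variance of that group's mean change. It is 0 with equal group sizes and equal variances.

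**2. The H1a test gives the same answer either way.** SE of the main effect = sqrt(1/224) = 0.0668.
- True rises of 0.4 (DV) and 0.2 (DNV): mean 0.3, difference 0.2.
- True rises of 0.3 and 0.3: mean 0.3, difference 0.
- In both cases the noncentrality is 0.3/0.0668 = 4.49 and power is 99.4% (noncentral t, 222 df).

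**3. A non-significant interaction would not show comparability.** SE = sqrt(2/112) = 0.1336, 222 df.

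| True DV-DNV difference | Non-significant, independent groups | Non-significant, yoked pairs |
|---|---|---|
| 0.2 SD | 68% | 62% |
| 0.3 SD | 39% | 30% |

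The last column assumes a within-pair correlation of 0.2 and a paired analysis of 112 pairs: SE = sqrt(2 x 0.8/112) = 0.1195, 111 df.

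**4. What an interval would show.** 90% CI half-width = 1.652 x 0.1336 = 0.22 SD for independent groups, or 0.20 SD for pairs as above. With two one-sided 5% tests and a true difference of zero, the smallest margin giving 80% power is (1.645 + 1.282) x 0.1336 = 0.39 SD.

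**5. Pooled, neutral, evocative and three-way terms.** Let Dn and De be the DV-DNV differences in alcohol-placebo change on neutral and evocative clips, in SDs of the per-stimulus change. The pooled WATCH term is (Dn + De)/2 and the three-way term is De - Dn.

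| Dn | De | Pooled WATCH term | Three-way term |
|---|---|---|---|
| 0 | 0.4 | 0.2 | 0.4 |
| 0.3 | 0.3 | 0.3 | 0 |
| -0.2 | 0.2 | 0 | 0.4 |

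- Row 1: the pooled term takes in half of an evocative-only difference. It would be significant 46%, 41% or 37% of the time if neutral and evocative change scores correlate 0.3, 0.5 or 0.7 (assumed).
- Row 2: the three-way term is zero although the evocative-clip change differs by 0.3. The two are equal only when Dn = 0.
- Row 3: the pooled term is zero although neither clip-specific difference is.

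**The case against.** The strongest defence is that Section 14 is the operative text. Its H1a asks only whether alcohol raises arousal, and the main effect answers that. This stands: the test is valid for that wording, and misreading arises only if the conclusion is drawn in Section 3's terms. But both wordings are current and carry the same label, so a reader of the results could take either.

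It can also be said that equality is a reasoned premise. Both groups meet the same drinking criteria (Section 5: "Because this is a study of the role of alcohol in IPV, all participants (DV & DNV) must") and share one target blood alcohol concentration (Section 11). That makes the premise plausible, but does not test it. Finally, the ANOVA will produce the partner type x beverage term in any case. This is true, and a significant result would count against comparability. Without an assigned hypothesis or criterion, though, a non-significant result has no agreed meaning.

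A reader might infer three stronger things that the documents do not support.
- **That H1b and H1c are biased.** They are not: each has its own term in the model, and neither depends on H1a being true.
- **That neutral clips isolate the alcohol effect, so that comparability is the same as Dn = 0.** H1a is not limited to neutral clips in either section. Neutral clips also show the partner (Section 12, Emotion-Regulation Task), and Section 4 expects partners in chronically aroused relationships to see threat in fairly neutral behaviour.
- **That the main effect can never carry any information about the difference.** Zero correlation needs equal group sizes and variances. Without these the estimates may be slightly correlated, but the main effect still does not estimate the difference.

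**Conclusion.** The point holds as a minor one. H1a as stated in Section 3 has no assigned test, and the test labelled H1a answers a different, narrower question. This conclusion is algebraic and needs none of the assumed inputs.

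The size of the problem with relying on a non-significant interaction does depend on assumptions about SD, alpha, independence and completeness. At true differences of 0.2 to 0.3 SD, it would be non-significant 68% to 39% of the time with independent groups, or 62% to 30% with pairs correlated 0.2. The H1c wording is a reconciliation point, not a fault in the three-way test.

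**What to change.** Keep the main effect as the check that alcohol raises arousal. Then choose one of the following.

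1. **Test what Section 3 says.** Assign the WATCH-trial partner type x beverage contrast to H1a. For each arousal variable, report the DV-DNV difference in alcohol-placebo change with a 90% CI. Show it separately for neutral and evocative clips as description. State that the pooled term includes half of any evocative-clip difference and that neutral clips also show the partner, so neither isolates a pure alcohol effect. Claim equivalence only against a margin justified in advance.
2. **Reword.** Restate H1a in Section 3 as alcohol increasing arousal, and draw no conclusion about comparability.

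In either case, reconcile the H1c statement in Section 3 with the two sentences in Section 14. Say that the three-way term tests the evocative-minus-neutral difference, and that it equals the evocative-clip DV-DNV difference only if the neutral-clip difference is zero.

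Option 2 costs only wording. Option 1 uses data and a model already planned. It adds a few reported estimates per arousal variable and makes comparability harder to claim: under the assumptions above, 112 per group gives 80% power for equivalence only at margins of about 0.39 SD or wider.

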Alcohol's Effect on Neurophysiological and Psychophysiological Arousal. Low to moderate alcohol exposure has been shown to lead to neurophysiological and psychophysiological responses consistent with increased arousal. Although alcohol is considered a pharmacological depressant, during the absorption phase, also known as the ascending limb of intoxication, and at peak Blood Alcohol Concentration (BAC), alcohol is actually arousing (Levenson, Sher, Newman, & Newlin, 1980; Schwartz et al., 1981). Electroencephalography (EEG) investigations of EEG frequencies aligned with a continuum of consciousness have found that during the ascending limb of intoxication, and at peak Blood Alcohol Concentration (BAC), alcohol is associated with increases in fast frequencies (beta and alpha; alertness and vigilance, and wakefulness, respectively) and decreases in slow frequencies (theta and delta; drowsiness, and sleep, respectively; Sanz-Martin et al., 2011). This pattern of increases in fast frequencies and decreases in slow frequencies are traditionally associated with cortical arousal and an activated state (Andreassi, 2000; Coult, 1998; Matousek & Petersen, 1983; Neidermeyer, 1998;;

Schwarz et al., 1981) and has been considered to be an index of arousal in both animals and humans (Hernandez-Gonzales et al., 2008; Sanz-Martin et al., 2011).

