EEG, Psychophysiology and Pupillary Response Acquisition - EEG and psychophysiology data will be collected using the BrainVision actiCHamp 64-channel, DC amplifier, 24-bit resolution, biopotential system. EEG data will be recorded with filters set at 1 and 30Hz, digitized at a sampling rate of 512Hz and stored on a computer using the PyCorder software. EEG data will be recorded to collect a 5-minute baseline measurement prior to administration of alcohol or placebo beverage. After beverage administration data will be collected for the duration of the emotion-regulation task (see below). To reduce confounding results due to artifacts, EEG signals will be examined for contamination by muscle activity and eye movement. Fast Fourier Transformation (FFT) analysis will be applied to 6-10 second epoch samples (corresponding to the delivery of stimuli) allowing for 1-s pre- and post-stimuli artifact subtraction with the spectral graph ranging from 0 to 30Hz at 0.5Hz-resolution. FFTs will be performed using EEGLab software to calculate 1) Absolute power (AP; power density of each frequency band expressed in microvolts squared; mV^2/Hz); 2) Relative power (RP; proportional contribution of each band to the total power across 1 – 30Hz). AP and RP will be transformed into Fisher's z-scores for statistical analyses. Skin conductance (SC) will be collected using the BrainVision GSR module with leads placed on the left index finger and left middle finger. SC will be recorded to collect a 5-minute baseline (as with EEG) measurement and for the duration of the emotion-regulation task and time-locked to evocative stimuli. SC data will be subjected to detrending and transformed to Fisher's z-scores for statistical analysis. Respiration and HRV will be measured using an integrated BrainVision respiration belt, and an EKG in Lead II position. As with EEG, baseline measures will be collected, and time locked to evocative events. EKG data will be quantified as respiratory sinus arrhythmia (RSA) which is a unique measure of parasympathetic activity and self-regulatory ability. Respiration and HRV data will also be transformed to Fisher's z-scores for statistical analysis. Pupillary response data will be collected using the EyeLink 1000 system high speed camera by SR Research (see sample data). Corneal reflection will be recorded at 250 Hz. The left and right pupil diameter measures will be averaged offline and baseline measures (1 sec prior to trial onset) will be subtracted. The difference between the maximum diameter during the trial and the baseline diameter will be calculated and transformed to Fisher's z-scores for statistical analysis. E-prime will control the flow of the emotion regulation task and generate timestamps to denote conditions for which all biopotential data can be analyzed.

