Specific Aim 2: To determine if alcohol induced arousal interferes with DV partners' ability to regulate emotion in response to evocative partner stimuli compared to DNV partners. All hypotheses will be tested using a 2 (beverage condition: alcohol vs. placebo) x 2 (stimulus: evocative vs. neutral) x 2 (regulation condition: WATCH vs. DON'T REACT) repeated measures ANOVA with a between-subjects factor (partner type: DV vs. DNV). Testing specific interactions within the overall model will test each hypothesis. If the ages of the DV and DNV partners are significantly different, ANCOVAs will be conducted as age may further moderate the relationships tested in Aim 2. To test the hypothesis that emotional regulation during evocative partner stimuli will be reduced compared to regulation during neutral stimuli (**Hypothesis 2a**), we will test the 2 (evocative vs. neutral) x 2 (WATCH vs. DON'T REACT) interaction term, collapsing across partner type in the placebo condition. To test the hypothesis

that emotion regulation during evocative partner stimuli will be reduced by alcohol, (**Hypothesis 2b**) we will test the 2 (evocative vs. neutral) x 2 (WATCH vs. DON'T REACT) interaction term collapsing across partner type in the alcohol condition. To test the hypothesis that DV partners are less able to regulate emotion during evocative stimuli than the DNV partners (**Hypothesis 2c**), we will test the 2 (DV vs. DNV) x 2 (evocative vs. neutral) x 2 (WATCH vs. DON'T REACT) in the placebo condition. Finally, to test the hypothesis that alcohol interferes with the ability to regulate emotion for DV partners compared to DNV partners (**Hypothesis 2d**), we will test the 2 (DV vs. DNV) x 2 (alcohol vs. placebo) x 2 (evocative vs. neutral) x 2 (WATCH vs. DON'T REACT) interaction.

15) **Provisions to Monitor the Data to Ensure the Safety of Subjects**

1. The experienced and qualified professionals responsible for determining serious adverse events in the proposed study “Emotions and Decisions of Couples” will be the PI and co-Investigator for the study [name]. and [name]. [name] has experience with both oral and intravenous alcohol administration and will work with [name] to identify any adverse events.

Any serious adverse events that do occur during the course of the study will immediately be reported to the University of New Mexico Human Research Protections Office as an adverse event.

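### Aim 1 is tested on several arousal outcomes with no primary outcome and no error control; with about 12 outcomes the false-positive chance per hypothesis is roughly 23–46%, not 5%

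*Combined protocol and SAP*

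**What the plan says.** Section 3 (Objectives) announces that "EEG, psychophysiology and pupillary response measurements of arousal will be collected during an emotion regulation task", which gives three measurement domains and no ranking among them.

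Section 14, Data Analysis Plan, Specific Aim 1, sets up one repeated-measures ANOVA (beverage by stimulus, with partner type between subjects) and assigns one effect to each hypothesis. For Hypothesis 1a, "we will examine the main effect of alcohol vs. placebo on arousal variables". Hypotheses 1b and 1c are tested on arousal, with no measure specified.

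Section 11, on EEG, psychophysiology and pupillary acquisition, describes what is processed for analysis. "FFTs will be performed using EEGLab software to calculate 1) Absolute power" is followed by relative power. Absolute power is the "power density of each frequency band expressed in microvolts squared", and the second metric is "Relative power (RP; proportional contribution of each band to the total power across" 1–30 Hz. Skin conductance, respiration, heart rate variability (quantified as RSA) and pupil dilation are also transformed for analysis. The system has 64 channels, and no electrode or region is specified. The bands are named only in section 4 (Background), which reports that alcohol produces "increases in fast frequencies (beta and alpha; alertness and vigilance, and wakefulness, respectively" and decreases in theta and delta.

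The Data Analysis Plan gives no significance level. Its one mention of significance is the Aim 2 age check ("If the ages of the DV and DNV partners are significantly different"). Section 9 (Study Endpoints) holds only a safety stopping rule.

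**The concern.** Each Aim 1 effect can be tested once per arousal measure, and nothing in the plan says which measure decides the hypothesis or what to conclude when measures disagree. Hypotheses 1b and 1c carry the study's main claim: that violent partners are more aroused than nonviolent partners by evocative displays, and more so after alcohol. As the plan stands, that claim could rest on one EEG band or one sensor while the other measures are null or point the other way. The background gives expected EEG directions (fast bands up, slow bands down), but the analysis section does not carry them into the tests, so the pattern that would count as support is also undefined.

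**Working it through.** The plan states no alpha, power or familywise error figure, so there is nothing of its own to reproduce.

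**Inputs**
- EEG: 2 metrics (section 11) × 4 bands (beta, alpha, theta, delta; section 4) = 8. That all four bands are tested separately is an assumption.
- Skin conductance 1, respiration 1, RSA 1, pupil 1 (section 11) = 4.
- Total m = 8 + 4 = 12, or 13 if heart rate, listed under the experimental tasks in section 12, is analysed on its own.
- A short count of m = 5: one EEG index plus the four others.
- Alpha: 0.05 two-sided per test, assumed. The isolated 0.05 in parentheses that appears in non-analysis parts of the text is attached to no test.
- Every null is taken as true.

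**Independent outcomes**

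At least one two-sided false positive: 1 − 0.95^m.
- m = 5: 1 − 0.95^5 = 22.6%
- m = 12: 1 − 0.95^12 = 46.0%, with 12 × 0.05 = 0.60 false positives expected
- m = 13: 1 − 0.95^13 = 48.7%, with 0.65 expected

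At least one false result in the predicted direction: 1 − 0.975^m.
- m = 5: 11.9%
- m = 12: 26.2%
- m = 13: 28.0%

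**Correlated outcomes**

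These outcomes will not be independent: relative powers share a common total, and respiration and RSA are linked. The calculation uses normal test statistics with a common pairwise correlation. For the directional columns, outcomes are signed so that higher means more aroused.

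| Correlation | m = 12, two-sided | m = 13, two-sided | m = 5, two-sided | m = 12, predicted direction | m = 5, predicted direction |
|---|---|---|---|---|---|
| 0 | 46% | 49% | 23% | 26% | 12% |
| 0.3 | 40% | 42% | 21% | 20% | 11% |
| 0.5 | 32% | 33% | 18% | 16% | 9% |
| 0.7 | 23% | 24% | 15% | 12% | 7% |

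The reference values for a single test are 5% two-sided and 2.5% in the predicted direction. Testing by channel or region would increase m and raise these figures.

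**Cost of adjusting**

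The smallest detectable group difference in a person-level contrast, 112 per group and 80% power, treating the groups as independent, is d = (z for alpha/2 + 0.842) × √(2/112), with √(2/112) = 0.1336.
- One outcome, alpha 0.05: (1.960 + 0.842) × 0.1336 = 0.37 SD
- First Holm step, 5 outcomes, alpha 0.05/5 = 0.01: (2.576 + 0.842) × 0.1336 = 0.46 SD
- First Holm step, 12 outcomes, alpha 0.05/12 = 0.00417: (2.865 + 0.842) × 0.1336 = 0.50 SD

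Later Holm steps are less strict, so the last two are upper limits.

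**The case against.** Several objections have force.

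- **The count is inferred.** The plan never lists its tested variables, and the four bands come from the background, which treats the pattern of fast-band increase with slow-band decrease as an index of arousal. One pattern-based EEG index is a possible reading. This stands, which is why the five-outcome figures are shown; they are still three to nearly five times the nominal 5%.
- **The hypotheses are directional.** A significant result in the wrong direction would not support 1b or 1c. This stands and roughly halves the figures, but the reference value halves too, to 2.5%.
- **Hypothesis 1a fits poorly.** The protocol itself expects alcohol to raise arousal in both groups, so an all-null calculation describes 1a badly. This stands; the weight falls on 1b and 1c.

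Three stronger readings are tempting, and the documents do not support them. A reader might infer that a false positive is more likely than not for each hypothesis, but every figure for 12 or 13 outcomes is below one half. A reader might extend the point to Aim 2. There, "Testing specific interactions within the overall model will test each hypothesis" describes one effect per hypothesis; the dependent variable is not named, and section 11 prepares a single averaged self-report rating. That is a separate gap and does not show many outcomes. Finally, a reader might say the plan lets any significant outcome decide. It states no decision rule at all; the fault is that nothing prevents this.

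**Conclusion.** The concern holds for Aim 1, mainly Hypotheses 1b and 1c. The plan provides several arousal outcomes, no primary outcome and no error control, and nothing elsewhere in the document supplies one. With about 12 outcomes the chance of at least one false positive per hypothesis is about 23–46% (up to 49% with 13), and about 12–26% in the predicted direction. With five outcomes it is about 15–23% two-sided. These figures rest on an assumed two-sided 0.05 level, an inferred outcome count, all nulls true and correlations between 0 and 0.7. The exact size is uncertain, but the inflation remains under every combination examined. This should be corrected before the data are analysed.

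**What to change.** In the Specific Aim 1 paragraph of the Data Analysis Plan, state alpha and do one of the following:

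1. Name one primary arousal outcome or one composite for each hypothesis. An EEG outcome needs its band, metric and electrode set stated. This returns the error to alpha per hypothesis.
2. Fix a short list (one EEG index on one stated electrode set, skin conductance, RSA, respiration, pupil), give the predicted direction of each, and apply Holm's procedure across the list within each hypothesis. This holds the familywise error at or below alpha per hypothesis.

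Holm alone does not settle conflicting outcomes. Under option 2, limit any claim to the outcomes that survive in the predicted direction, and report all listed outcomes, including discordant ones. Under either option, label other bands and channels exploratory. Name the Aim 2 dependent variable, and apply the same rule there only if more than one is used.

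The change is to plan wording only. Under option 2 with five outcomes, the smallest detectable group difference for a single outcome rises from about 0.37 SD to at most 0.46 SD. Option 1 has no such cost.
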